### 7.2 Intervention - Visits 2-9 (1 hour)

- Determine any changes in medications or concurrent conditions
- Assess pain intensity, unpleasantness, qualitative aspects of pain

Assess spatial extent of pain  
Continue intervention (TPD training or Control)  
Assess pain intensity, unpleasantness, qualitative aspects of pain  
Assess spatial extent of pain

**7.3. Intervention+Completion - Visit 10 (up to 3 hours)**

Assess pain intensity, unpleasantness, qualitative aspects of pain  
Assess spatial extent of pain  
Final intervention (TPD training or Control)  
Assess two-point/single-point discrimination  
Assess pain intensity, unpleasantness, qualitative aspects of pain  
Assess spatial extent of pain  
Administer psychological questionnaires

Note that some of the procedures above may be omitted for the purpose of streamlining the study visits, or if procedures are deemed to be incongruent with the participants' ongoing clinical treatments. Omitting these procedures would reduce participant burden and would have no impact on safety.

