### **6.5 Psychological Assessment/Questionnaires**

Variation in psychological states can contribute substantially to the construction of the experience of pain, and may importantly influence attentional processes related to pain. Thus, participants will undergo extensive psychological characterization with a particular focus on variables known to influence pain. Many scales will be useful for enabling comparisons of these patients with chronic pain patients in other studies, and are part of our standard testing battery.

Anxiety: The PROMIS Anxiety pediatric scales will be used to assess anxiety. The SCARED anxiety scale will be used to further characterize anxiety.

Mood and Affect: The PROMIS Depression pediatric scales will be used to assess depression. The Positive and Negative Affect Schedule - Expanded will be used to characterize mood and affect.

Mindfulness: The Freiburg Mindfulness Inventory will be used to assess mindfulness.

Impulsivity: The Barratt Impulsiveness Scale will be used to assess impulsivity.

Handedness: The Edinburgh Handedness Inventory will be used to assess the degree of handedness and will be critical in the interpretation of differences in the lateralization of nociceptive processing.

Sleep: Sleep deprivation may substantially alter pain sensitivity. The Epworth Sleepiness Scale will be used to quantify the level of daytime sleepiness, while the Pittsburgh Sleep Quality Index will be used to assess sleep quality.

Pain Interference, Disability, and Catastrophizing: The PROMIS Pain Interference Scale (pediatric version) will be used to assess how much pain interferes with daily living. Pediatric versions of the pain catastrophizing scale will be used to assess pain-related catastrophizing, while the Functional Disability Index will be used to characterize disability.

Social Status and Discrimination: Insurance, income, education level, and experience of discrimination will be used to quantify socio-economic variables.

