### 7.1 Baseline + Intervention - Visit 1 (up to 3 hours)

- Completion of informed consent/assent prior to initiation of study procedures
- Obtain information for payment, provide ClinCard
- Randomize to intervention
- Review medical history
- Document all concomitant medications including prescribed, over the counter, and nutraceutical supplements
- Administer questionnaires
- Assess pain intensity, unpleasantness, qualitative aspects of pain
- Assess spatial extent of pain (body map or patient's own photo)
- Demonstration of two-point/single-point discrimination procedure
- Assess two-point/single-point discrimination
- Initiate intervention (TPD training or Control)
- Assess pain intensity, unpleasantness
- Assess spatial extent of pain

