## 11. ETHICS AND HUMAN PARTICIPANTS CONSIDERATIONS

### 11.1 Potential Risks and Minimization of Risk

Psychological Distress. There is a chance that participation in this study could cause psychological distress. The psychological questionnaires could make some participants uncomfortable.

Sensory Testing. The sensory stimuli will consist of innocuous tactile stimuli delivered for the two-point discrimination as well as the one point attentional control conditions. These stimuli are similar to those utilised during clinical practice and encountered during daily life, and pose minimal risk. Specifically, application of these stimuli to pain-free areas would never be expected to generate pain or cause tissue damage. In patients, testing in zones of chronic pain could possibly increase ongoing pain or could produce prolonged aftersensations. Testing in these zones is fully optional; if testing exacerbates pain, the participant can choose for the testing to be undertaken in a pain-free area, or testing can be immediately terminated if requested.

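### The only end-of-study tactile threshold test follows the last training session while the baseline test precedes all training, so the threshold change cannot separate same-day practice from retained change

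*Protocol*

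**What the plan says.** Protocol 7.1 (Visit 1) lists "Administer questionnaires", then pain and its spatial extent, then a demonstration, then "Assess two-point/single-point discrimination", and only after that "Initiate intervention (TPD training or Control". Pain and its extent are then rated again.

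Protocol 7.2 (Visits 2-9) places pain and extent ratings on both sides of "Continue intervention (TPD training or Control". It lists neither thresholds nor questionnaires.

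Protocol 7.3 (Visit 10) lists pain and extent, then "Final intervention (TPD training or Control", then the discrimination test, then pain and extent again, and last "Administer psychological questionnaires". The opening of Section 7 carries this list over to whichever visit turns out to be the final one. No later visit is planned.

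Section 5.1 describes two-point training as a caliper threshold procedure with immediate feedback. Section 5.2 gives the control arm a small-versus-large probe judgement, also with feedback, at the same sites. Section 9.1 (Aim 2) treats improvement in thresholds as a control variable, for possible use as a covariate or a manipulation check. The Aim 2 outcomes are pain area, pain intensity and unpleasantness, and disability. Disability is measured within the questionnaires: "the Functional Disability Index will be used to characterize disability" (Section 6.5).

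**The concern.** A first-to-last change in threshold is easy to interpret only if both readings are taken in the same state. Here the first is taken untrained and the last directly after a feedback session in the visit order. The two arms have also just practised different things. Randomisation and a control arm remove whatever is common to both arms, but not a warm-up on the caliper task that only one arm receives. The single-point measure has the mirror problem, since there it is the control arm that is freshly rehearsed.

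The threshold change is what would link training to the proposed mechanism, retuned spatial processing. If same-day rehearsal alone can produce it, a positive manipulation check does not show that the earlier sessions changed anything. A covariate built from it carries the same ambiguity. An analysis plan cannot repair this, because the reading that is needed is never taken.

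**Working it through.** No figure stated in the protocol is at issue, so the main check sets the visit lists side by side.

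| Measure | Visit 1 (7.1) | Visits 2-9 (7.2) | Visit 10 (7.3) |
|---|---|---|---|
| Thresholds | before training only | none | after training only |
| Questionnaires, including disability | before training only | none | after training only, last item |
| Pain intensity, unpleasantness, extent | before and after | before and after | before and after |

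The lists are not expressly called sequential. However, each places pain ratings on both sides of training, which makes sense only if the order is meant.

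**Thresholds.** Let R be the retained change and W the same-day warm-up on the two-point task. With the test before training at Visit 1 and after it at Visit 10:

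- two-point arm: expected change = R(two-point) + W(two-point)
- control arm: expected change = R(control) + W(control)
- difference between arms = [R(two-point) − R(control)] + [W(two-point) − W(control)]

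The second bracket vanishes only if both arms warm up equally on the tested task. Sections 5.1 and 5.2 give them different tasks, so there is no reason to expect that. With one final reading per participant the two brackets cannot be estimated separately.

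**Pain outcomes.** Pre-training values exist at both visits, so Visit 10 before training minus Visit 1 before training is available and contains no same-day term.

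**Scale, for illustration only.** Inputs: 20 per arm (Section 9.2) and p<0.05 (Section 9.3, two-sided assumed). Further assumptions: no retained difference between arms; a warm-up gain of d SDs of the change score in the two-point arm and none in control; a two-sample t-test on threshold change.

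- Degrees of freedom = 20 + 20 − 2 = 38.
- Noncentrality = d × √(20/2) = d × √10.
- Chance of a significant difference = P(|T| > t critical), with T noncentral t on 38 df.

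| Assumed d | Noncentrality | Chance of significance |
|---|---|---|
| 0 | 0 | 5% |
| 0.2 | 0.63 | about 9% (0.095) |
| 0.3 | 0.95 | about 15% (0.152) |
| 0.5 | 1.58 | about 34% (0.338) |

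A normal approximation gives about 10%, 16% and 35% for the same three gains. The protocol gives neither a warm-up gain nor an SD for thresholds, so the range is not a prediction.

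**The case against.** The strongest reply is that thresholds are not an efficacy outcome. Section 9.1 only permits their use as covariate or manipulation check, so a distorted threshold change would not by itself create a false efficacy result. That stands, and it limits the weight of the point. Testing after the full course is also a defensible choice, and Aim 2 does not speak of lasting effects; the interest in retained change is inferred from the retuning rationale. It is also true that moving the test removes only the same-day component. After nine feedback sessions the two-point arm would still be more practised at the tested task than the control arm.

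A reader might infer two stronger things, and the protocol supports neither.

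- *That the pain outcomes are confounded as well.* Section 11.1 says that "testing in zones of chronic pain could possibly increase ongoing pain or could produce prolonged aftersensations", which suggests that a flare after the session could hide a benefit. But pre-training ratings are taken at every visit, and Section 9.1 does not fix a contrast of post-training Visit 10 against pre-training Visit 1.
- *That the disability result is contaminated by practice.* Rehearsing a caliper task does not carry over to a disability questionnaire. A flare is possible, but testing in painful zones is optional, both arms are stimulated at the same sites, and any effect common to both cancels in the time-by-group term. The order mismatch exists for disability, but its consequence is weaker and not demonstrated.

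None of this answers the threshold point itself: the arms rehearse different tasks just before the only final test, and no second reading exists to separate the effects.

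**Conclusion.** The point holds for thresholds. Under the order in 7.1 and 7.3, the change from first to last test combines retained change with an immediate practice gain that can differ by arm, and no later analysis can separate them. It affects the manipulation check or covariate, not the Aim 2 efficacy outcomes directly. Its size cannot be derived from the protocol; the 9%, 15% and 34% figures rest wholly on the assumed gains of 0.2, 0.3 and 0.5 SD in one arm only, on no retained difference, and on a simple t-test in place of the planned mixed model. The conclusion also assumes that the visit lists give the order of procedures. Pain intensity, unpleasantness and area are not confounded by the order. For the questionnaires, including disability, the mismatch is real but its effect is not shown. This is a cheap improvement worth making, not a flaw that undermines the trial.

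**What to change.** In Protocol 7.3, move the two-point/single-point discrimination test to before the final training session, so that it matches 7.1. For the same like-for-like timing, move the questionnaires there too. The same order should hold when the final visit comes early under Section 7.

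No procedure is added; lines in one visit list change places. The cost is that, with ten visits, thresholds and disability would reflect nine training sessions instead of ten. Any advantage the two-point arm has gained from task practice accumulated over earlier sessions would remain, so a threshold gain should still be reported with that caveat.

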**8. SAFETY ASSESSMENTS AND MONITORING**

This study involves no increase over minimal risk, so a Data Safety Monitoring Board will not be created for this study. Any adverse events related to the study procedures will be reported to Cincinnati Children's Hospital Medical Center's Institutional Review Board.

**9. STATISTICS**

**9.1 Statistical Analysis Plan**

**Aim 1:**

A mixed model analysis of variance will be utilized to determine differences between groups (chronic pain patients vs. healthy controls - between factor) and body site (within factor), and group X body site interactions.

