## **2 SIGNIFICANCE AND INNOVATION**

### **2.1 Scientific Premise**

Highly disabling persistent pain is a frequent complaint in children, with prevalence estimated at approximately five percent in Western societies (Huguet and Miro, 2008; Hechler et al., 2014). Pain prevalence rates increase with age (King et al., 2011) and as such, chronic pain in adolescence represents a significant economic problem in the USA (Groenewald et al., 2014). Adolescence is a critical period for development physically, psychologically and socially, and pain severely interferes with such an important phase of life (O'Sullivan et al., 2012). Adequate management of pain in adolescents should clearly be a goal in itself, but the evidence suggests that management of pain in young people may also help prevent pain in adults (Hestbaek et al., 2006).

From a mechanistic standpoint, fundamental questions about pain remain unanswered, and this has meant the treatment needs of pain sufferers have largely been unmet. To date the intensity of pain has been a focus of investigation and

treatment, but pain intensity is only one dimension of the pain experience. Research into the spatial dimension of pain has been grossly neglected in comparison; we still do not fully understand how the nervous system processes and spatially tunes incoming sensory information from the body. This avenue of inquiry is critical, given that one of the most common and intriguing symptoms of chronic pain is the spread of pain well beyond the site of the original injury. Our knowledge of sensory function in adolescents is particularly lacking.

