## **3 STUDY DESIGN**

Prior to commencing this investigation we will optimize the tactile discrimination threshold testing (i.e. as per baseline visit, below), and the training conditions, in up to ten participants (patients and/or healthy controls). This will serve as a pilot to refine operational aspects of study procedures before we commence the main investigation proposed herein. Following this, youth with either chronic pain (ages 10-17, n=40) or healthy youth (ages 10-17, n=20) will undergo assessments of two-point and single-point discrimination thresholds in an initial session (Aim 1). After this initial session, youth with chronic pain will participate in up to 9 additional sessions of attentional training (Aim 2). These chronic pain patients will be randomized to either two-point discrimination training (n=20) or a single-point spatially-directed attentional control condition (n=20). Participants will not be informed of which intervention they will receive (single-blind study). Psychological questionnaires will be completed in the first and last sessions in order to determine how these variables relate to tactile discrimination and response to training.

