## 6 STUDY PROCEDURES AND MEASURES

### 6.1 Study Recruitment/Enrollment Procedures

The primary methodology for identifying and recruiting chronic pain patients for this study will be through identification of potential participants from the inpatient and outpatient chronic pain clinics at Cincinnati Children's Hospital Medical Center, as well as community advertisements. Over the course of this project, we will enroll up to 50 patients.

Healthy control participants will be identified via word-of-mouth recruitment as well as advertisements throughout the community. We will enroll up to 30 healthy control participants.

Methods and processes for identifying patients will be conducted in accordance with the Declaration of Helsinki and Good Clinical Practice Guidelines.

To support our recruitment and retention, progress will be evaluated weekly and existing challenges and potential solutions will be discussed with the study team to ensure we meet our projected timeline.

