### **6.3 Participant Characterization**

Medical History: A medical history will be completed to capture pain diagnosis, medication usage, and concurrent conditions. This will be augmented and crossreferenced with information from the participant's medical record.

Body Morphometry: Height, weight, and hip and waist circumference will be obtained.

Menstrual Cycle: Position in the menstrual cycle will be noted by onset of last menstrual period in women who are not on oral contraceptives. For women on oral contraceptives, the phase of the cycle will be determined by the contraceptive pill packet.

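### The Aim 1 comparison of patients with healthy controls is not randomised, describes no matching and has no age or sex term, so an age or sex imbalance would enter the group effect

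*Protocol*

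**What the plan says.** Protocol Section 9.1, which is itself titled as the statistical analysis plan, gives the Aim 1 model in one sentence. It is a mixed analysis of variance for "differences between groups (chronic pain patients vs. healthy controls - between factor) and body site (within factor"), together with the interaction of group and body site. No other term appears. Covariates are mentioned only in the following paragraph, for Aim 2. There they are optional, and they consist of improvement in tactile thresholds and questionnaire data.

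Section 3 sets the sizes and age range: "youth with either chronic pain (ages 10-17, n=40) or healthy youth (ages 10-17, n=20) will undergo assessments". Randomisation is described only for the patients, between the two Aim 2 training conditions.

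On recruitment, Section 6.1 says: "Healthy control participants will be identified via word-of-mouth recruitment as well as advertisements throughout the community". Patients come primarily from "inpatient and outpatient chronic pain clinics", and also from community advertisements. Section 4.1 admits controls of either sex aged 10 to 17 who are in good general health and fluent in English. It sets no age or sex quota.

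Two further statements bear on the point. Section 2.1 notes: "Pain prevalence rates increase with age". Section 6.3 says of body size: "Height, weight, and hip and waist circumference will be obtained".

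**The concern.** Aim 1 asks whether chronic pain in youth goes with disrupted spatial tuning. The answer is the group term in the model, and for that term the study is an observational comparison. An imbalance between patients and controls can be limited by design, through matching or recruitment quotas, or handled in the analysis, through covariates. The protocol describes neither.

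The age range covers eight years of childhood and adolescence, and the outcome is a distance on the skin. If the groups differ in age or sex, and the threshold varies with that characteristic, the model attributes the resulting difference to chronic pain. Depending on the two directions, this could produce an apparent deficit or hide a real one.

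**Working it through.** **Plan's own figure.** Section 9.2 chooses 20 per group by a heuristic and gives no effect size, SD or power. There is nothing to reproduce, and this point does not dispute the sample size.

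**Inputs from the protocol.** 40 patients and 20 controls (Section 3); ages 10 to 17 (Section 4.1); p<0.05 (Section 9.3), taken as two-sided.

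**Assumptions, not in the protocol.**
- Age SD within group: ages spread evenly from 10 up to 18 give 8/√12 = 2.3 years.
- Mean age gap between groups: 1 to 2 years.
- Within-group correlation r of threshold with age: 0.2 to 0.4 in absolute value.
- One threshold value per person.

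**Step 1: bias.** With no true effect of pain, the spurious standardised difference is d = r × (gap / 2.3).
- Low end: 0.2 × 1/2.3 = 0.087 SD.
- High end: 0.4 × 2/2.3 = 0.348 SD.

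**Step 2: false-positive rate.** The standard error of a standardised difference is √(1/40 + 1/20) = √0.075 = 0.274. The noncentrality is d/0.274, which runs from 0.32 to 1.27. The two-sided 5% t test on 58 degrees of freedom then rejects as follows.

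| Age gap | r = 0.2 | r = 0.3 | r = 0.4 |
|---|---|---|---|
| 1 year | 6.1% | 7.5% | 9.6% |
| 2 years | 9.6% | 15.5% | 23.9% |

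At r = 0.1 with a 1-year gap the rate is 5.3%. With no gap or no correlation it is 5%. Sex works through the same product of imbalance and correlation, but the protocol offers nothing from which to set a range for it.

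**Step 3: does a covariate remove the bias?** This was simulated with 4,000 trials per scenario, imbalances of 0.5 to 1.0 SD and r of 0.3 to 0.5, a range that reaches stronger correlations than Step 2. The unadjusted test rejected in 9% to 43% of null trials. With the covariate in the model it rejected in 5.0% to 5.4%. Masking also occurs. With a true difference of 0.77 SD, an opposing imbalance of 0.5 SD and r = 0.3, power was 60% unadjusted and 80% adjusted.

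**Step 4: what adjustment does to precision.** The variance of the adjusted difference, in units of the threshold variance, is (1 − r²) × [1/40 + 1/20 + (gap/2.3)²/58]. For a 2-year gap and r = 0.2 this is 0.96 × (0.075 + 0.013) = 0.0845, against 0.075 unadjusted. The difference detectable at 80% power is 0.78 SD unadjusted. Adjusted, it becomes:

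| Age gap | r = 0.2 | r = 0.3 | r = 0.4 |
|---|---|---|---|
| 1 year | 0.78 | 0.76 | 0.73 |
| 2 years | 0.83 | 0.81 | 0.77 |

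Adjustment can therefore narrow or widen the interval slightly, depending on the imbalance.

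**The case against.** The strongest objection is that the size of the bias rests wholly on assumption. No part of the protocol says that two-point thresholds vary with age, sex or body size, and none gives the ages to be expected in either group. The 24% needs the largest gap and the strongest correlation together, and the low end is trivial. This stands, so the figures show only what is possible.

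A reader might infer from the prevalence remark in Section 2.1 that patients will be older. That remark describes a population trend without a gradient within 10 to 17, and it says nothing about which healthy volunteers respond. It makes an older patient group plausible but does not establish one.

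A reader might also infer that the two groups come from separate sources. They do not: Section 6.1 uses community advertisements for both, so the sources partly overlap.

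The Aim 1 sentence is also short and does not exclude covariates, and a separate analysis plan may exist that adds them. That is fair. But Section 9.1 names the model terms, and it raises covariates for the randomised comparison while naming none for the non-randomised one. The gap is in what this document states.

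Finally, Section 9.2 presents the study as a first investigation intended to learn effect size and variability. That lowers the stakes of a single p-value. It does not remove the problem, because a confounded group difference is also a poor effect-size estimate.

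**Conclusion.** The point holds at moderate strength. As stated, the Aim 1 model offers no protection against an age or sex difference between non-randomised groups, and no matching is described that would supply it. Under the assumed gaps and correlations the false-positive rate is about 6% to 24%. If either quantity is small it is close to 5%. The direction of any bias is unknown.

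Two stronger readings are not supported. One is that an Aim 1 difference would be an artefact of recruitment: the protocol shows only that the stated model could not tell the two explanations apart. The other is that adjustment would also sharpen the test: under the same imbalance that creates the bias, the detectable difference ranges from 0.73 to 0.83 SD against 0.78 unadjusted, so no gain can be promised.

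**What to change.** In Section 9.1, Aim 1, add age and sex as fixed covariates in the mixed model, and name the adjusted group difference with its 95% CI as the Aim 1 result.

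Use a body-size measure only in a sensitivity analysis. It is likely to track age in this range. Although Section 6.3 says it will be obtained, it is not in the Visit 1 list in Section 7.1, so it may not be complete. With 20 controls the main covariate list should stay short.

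In Section 6.1, where feasible, recruit controls to the age-band and sex distribution of the patients. This has to be arranged before the controls are enrolled.

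The cost is one sentence in each section, about 2 degrees of freedom and, if the groups turn out unbalanced on age, possibly a slightly wider interval. Age must be known to confirm eligibility, and sex should be known at enrolment, so no new measurement is needed. Adjustment handles only these measured characteristics; other differences between patients and volunteers remain.
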